5.3 General Concomitant Medication and Supportive Care Guidelines

The following medications **are prohibited**:

- 1. Other anti-cancer therapy while on treatment in this study. NOTE: megestrol (Megace) if used as appetite stimulant is allowed and palliative radiation therapy can be permitted with the approval of the principal investigator.
- 2. Use of other investigational drugs within 28 days (or five half-lives whichever is shorter; with a minimum of 14 days from the last dose) preceding the first dose of GSK1120212 and GSK2141795during the study.
- 3. All medications in Appendix E are prohibited and those listed in Appendix F are to be used with caution.
- 4. Concurrent treatment with bisphosphonates is permitted; however, treatment must be initiated prior to the first dose of study therapy. Prophylactic use of bisphosphonates in subjects without bone disease is not permitted, except for the treatment of osteoporosis.
- 5. Subjects should abstain from taking any herbal and dietary supplements within 5 half lives (or 14 days if the drug is a potential enzyme inducer) prior to the first dose of either study drug until completion of the follow-up visit.

Because the composition, pharmacokinetics and metabolism of many herbal supplements are unknown, the concurrent use of all herbal supplements is prohibited during the study (including but not limited to St. John's wort, kava, ephedra (ma huang), gingko biloba, dehydroepiandrosterone (DHEA), yohimbe, saw palmetto, or ginseng).

The investigator should contact the study PI before initiating treatment with any herbal preparation.

- 6. Growth factor support is allowed only with the permission of the principal investigator.
- 7. Oral steroids should be used with caution and subjects monitored for steroid-induced hyperglycemia. Short courses (up to a maximum of 14 days) of oral corticosteroids intended to treat study treatment related rash or diarrhea are allowed. Budenoside is recommended for supportive care of diarrhea. Subjects will be instructed to inform the investigator before taking any of these or any other medications. Investigators (or his/her appropriate designee) will be expected to review concomitant medications with the subject at each clinical visit.

Drugs to be used with Caution with GSK1120212 and GSK2141795 are listed in Appendix F (the interactions with p450 for GSK2141795 in the in vitro studies are at much higher concentrations than with GSK1120212).

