10.1 Antitumor Effect– Solid Tumors

For the purposes of this study, participants should be re-evaluated for response every 2 cycles (+/- 1 week), which should be completed prior to the participant initiating the next cycle. In addition to a baseline scan, confirmatory scans should also be obtained at least 4 weeks following initial documentation of objective response. The next scheduled restaging scan may be used as the confirmatory scan.

Response and progression will be evaluated in this study using the new international criteria proposed by the Response Evaluation Criteria in Solid Tumors (RECIST) (Eisenhauer et al, 2009) guideline version 1.1. Changes in the diameter (unidimensional measurement) of the tumor lesions are used in the RECIST criteria.

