10.1.2 Disease Parameters

Measurable Disease

Measurable disease is the presence of at least one (1) lesion that can be accurately measured in at least one dimension with longest diameter > 20 millimeters (mm) using conventional techniques (CT, MRI, x-ray) or ≥ 10 mm with spiral CT scan. Measurable lesions must be at least 2 times the slice thickness in mm. All tumor measurements must be recorded in millimeters (or decimal fractions of centimeters).

Lesions situated in a previously irradiated area will be considered measurable if there is objective evidence of progression of the lesion prior to study enrollment. Lesions in previously irradiated areas must be clearly identified as such.

Malignant lymph Nodes

To be considered pathologically enlarged and measurable, a lymph node must be ≥ 15 mm in short axis when assessed by CT scan (CT scan slice thickness recommended to be

no greater than 5 mm). At baseline and in follow-up, only the short axis will be measured and followed.

Non-measurable Disease

All other lesions (or sites of disease), including small lesions (longest diameter <10 mm or pathological lymph nodes with \geq 10 to < 15mm short axis, are considered non-measurable disease. Bone lesions, leptomeningeal disease, ascites, pleural/pericardial effusions, lymphangitis cutis/pulmonis, inflammatory breast disease, abdominal masses identified by physical exam that are not measurable by reproducible imaging techniques, and cystic lesions are all considered non-measurable.

Target Lesions

All measurable lesions up to a maximum of 2 lesions per organ and 5 lesions in total, representative of all involved organs, should be identified as target lesions and recorded and measured at baseline. Lesions must be accurately measured in 1 dimension with a minimum size of 10 mm by CT or MRI (slice thickness no greater than 5 mm), 20 mm by *chest* x-ray. Nodes must have a short axis ≥ 15 mm. The short axis should be included in the sum of the lesions in the calculation of response. Nodes that shrink to < 10 mm are considered normal. Target lesions should be selected on the basis of their size, be representative of all the involved organs, and should be lesions that can be followed with reproducible repeated measurements.

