Lytic bone lesions or mixed lytic-blastic lesions, *with identifiable soft tissue components*, that can be evaluated by cross sectional imaging techniques such as CT or MRI can be considered target lesions if the *soft tissue component* meets the definition of measurability as defined above. Cystic lesions thought to represent cystic metastases can be considered as target lesions. However, if non-cystic lesions are present, these are preferred for selection as target lesions. Lesions in previously irradiated areas or areas subject to other loco-regional therapy are usually not considered measurable unless there has been demonstrated progression of that lesion.

Non-target Lesions

All other lesions, including small lesions < 10 mm or pathological lymph nodes measuring \geq 10 mm to < 15 mm in short axis, as well as truly non-measurable lesions, which include leptomeningeal disease, ascites, pleural or pericardial effusion, inflammatory breast disease, lymphangitic involvement of skin or lung, abdominal masses identified by physical exam that are not measurable by reproducible imaging techniques.

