10.3 Response Criteria

10.3.1 Evaluation of Target Lesions

Complete Response (CR):

Disappearance of all target lesions. Any pathological lymph node must have reduction in short axis to < 10 mm.

Partial Response (PR):

At least a 30% decrease in the sum of the diameters of target lesions, taking as reference the baseline sum diameters.

Progressive Disease (PD):

At least a 20% increase in the sum of the diameters of target lesions, taking as reference the smallest sum on study with at least a 5 mm absolute increase in the sum of all lesions. The appearance of one or more new lesions* denotes disease progression.

Stable Disease (SD):

Neither sufficient shrinkage to qualify for PR nor sufficient increase to qualify for PD, taking as reference the smallest sum diameters while on study.

Unknown (UN):

Assessment of target lesions cannot be made due to insufficient or unevaluable data. In this case, a concise explanation must be given.

Note: If tumor response data is missing for target lesions, the overall assessment must be UN unless there is new disease that would result in an overall assessment of PD. However, if there is missing or unevaluable data for non-target lesions, but data is available for all target lesions, the overall response for that time point will be assigned based on the sum LD of all target lesions. Additionally, the assessment of CR cannot be made if there is missing or unevaluable data for non-target lesions. In this case, the overall assessment would be PR.

*Definition of New Lesion: The finding of a new lesion should be unequivocal (i.e. not due to difference in scanning technique, imaging modality or findings thought to represent something other than tumor (ex: new bone lesions may be healing or flare of pre-existing lesions). However, a lesion identified on a follow-up scan in an anatomical location that was not scanned at baseline is considered new and will indicate PD. If a new lesion is equivocal (because of small size, etc.), follow-up evaluation will clarify if it truly represents new disease and if PD is confirmed, progression should be declared using the date of the initial scan on which the lesion was discovered.

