10.3.3 Evaluation of Best Overall Response

The best overall response is the best response recorded from the start of the treatment until disease progression/recurrence (taking as reference for progressive disease the smallest measurements recorded since the treatment started). The participant's best response assignment will depend on the achievement of both measurement and confirmation criteria.

For Participants with Measurable Disease (i.e., Target Disease)						
Target Lesions	Non-Target Lesions	New Lesions	Overall Response	Best Overall Response for when Confirmation is Required:		
CR	CR	No	CR	> 4 wks confirmation		
CR	Non-CR/Non-PD	No	PR			
CR	Not evaluated	No	PR	≥ 4 wks confirmation		
PR	Non-CR/Non-PD/Not evaluated	No	PR			
SD	Non-CR/Non-PD/Not evaluated	No	SD	Documented at least once > 4 wks from baseline		
PD	Any	Yes or No	PD			
Any	PD*	Yes or No	PD	No prior SD, PR or CR		
Any	Any	Yes	PD			

* In exceptional circumstances, unequivocal progression in non-target lesions may be accepted as disease progression.

Note: Participants with a global deterioration of health status requiring discontinuation of treatment without objective evidence of disease progression at that time should be reported as "symptomatic deterioration". Every effort should be made to document the objective progression even after discontinuation of treatment.

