14.4.2 Evaluation of Response

All participants included in the study must be assessed for response to treatment, even if there are major protocol treatment deviations or if they are ineligible. Each participant should be assigned one of the following categories: 1) complete response, 2) partial response, 3) stable disease, 4) progressive disease, 5) early death from malignant disease, 6) early death from toxicity, 7) early death because of other cause, or 9) unknown (not assessable, insufficient data). By arbitrary convention, category 9 usually designates the "unknown" status of any type of data in a clinical database.

All participants who have measurable disease present at baseline, have received at least one cycle of therapy, and have had their disease re-evaluated will be considered evaluable for response. Participants in response categories 5-9 will not be considered evaluable but will remain within the intention to treat analysis.

Participants who develop brain metastasis on study, but continue on study after definitive treatment of their cranial disease, will be considered to have had progressive disease at the point of the diagnosis of the initial brain metastasis.

All conclusions should be based on all evaluable participants. Subanalyses may then be performed on the basis of a subset of participants, excluding those for whom major protocol deviations have been identified (e.g., early death due to other reasons, early discontinuation of treatment, major protocol violations, etc.). However, these subanalyses may not serve as the basis for drawing conclusions concerning treatment efficacy, and the

reasons for excluding participants from the analysis should be clearly reported. The 95% confidence intervals should also be provided.

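### Palliative radiation is allowed on study, but outside the brain no rule clearly keeps shrinkage of an irradiated target lesion out of the primary response rate

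*Combined protocol and SAP*

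**What the plan says.** Section 5.3 prohibits other anti-cancer treatment while on study treatment, with the exception that "palliative radiation therapy can be permitted with the approval of the principal investigator". It attaches no condition about target lesions and no consequence for the endpoint.

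Section 10.3.1 defines partial response as "At least a 30% decrease in the sum of the diameters of target lesions, taking as reference the baseline sum diameters". Section 10.3.3 sets the window: "The best overall response is the best response recorded from the start of the treatment until disease progression/recurrence". Section 10.1 adds that "confirmatory scans should also be obtained at least 4 weeks following initial documentation of objective response".

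Section 10.1.2 mentions irradiated lesions twice:
- Under measurable disease: "Lesions situated in a previously irradiated area will be considered measurable if there is objective evidence of progression of the lesion prior to study enrollment".
- Under target lesions: "Lesions in previously irradiated areas or areas subject to other loco-regional therapy are usually not considered measurable unless there has been demonstrated progression".

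One endpoint rule covers participants who continue after local treatment on study. Under Section 14.4.2, those who develop a brain metastasis and stay on study after its treatment "will be considered to have had progressive disease at the point of the diagnosis of the initial brain metastasis".

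Section 14.2 makes the response rate the primary endpoint of this single-arm trial of 35 participants. The 7% null is rejected at 5 or more responders.

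**The concern.** Read together, these sections leave a path for error. Suppose a participant has a pelvic or nodal target lesion irradiated for symptoms, with approval and without progression. The lesion stays in the target sum. If the sum falls by 30% and the fall holds for four weeks, the stated criteria give a confirmed partial response, although radiation may have produced it.

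There is no control arm in which such responses would also appear. The error can only add responders. With a cut-off of 5 and 2.45 responders expected under the null (35 × 0.07), a single misclassified participant matters. If the handling is left open until the data are in, it will be settled after it is known which responders were irradiated.

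**Working it through.** **Does any existing rule close the gap?**
- *Irradiated-lesion text, Section 10.1.2.* The first sentence concerns progression before enrollment. The second belongs to the selection of target lesions at baseline and says only that such lesions are usually not measurable. Neither says what happens when a selected target is irradiated later.
- *Unknown category, Section 10.3.1.* It is for insufficient or unevaluable data. An irradiated lesion can still be measured, and the text does not link the category to radiation.
- *Confirmation, Section 10.1.* A second scan tests whether shrinkage lasts, not what caused it.
- *Imaging-core review, Section 10.3.6 and Appendix H.* The listed package is the baseline, response and confirming scans with their radiology reports. It contains no radiation record.
- *Brain metastases, Section 14.4.2.* Progression is assigned at diagnosis, so the window does close, but for this site only.

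**The plan's own design (Section 14.2).** n = 35, reject at 5 or more, p0 = 0.07, p1 = 0.22, exact binomial.
- Type I error = P(X ≥ 5 | 35, 0.07) = 0.0948. The plan states 0.09, which matches after rounding to two decimals.
- Power = P(X ≥ 5 | 35, 0.22) = 0.910. The plan states 91%, so the figure is reproduced.

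**Sensitivity when radiation frequency is unknown.** Let *a* be the share of participants with a target lesion irradiated on study, and *c* the share of those, among participants who would not otherwise respond, who then meet partial response. Both are assumptions. At a true drug response rate of 7%, the apparent rate is p = 0.07 + 0.93 × a × c, and the chance of rejecting is P(X ≥ 5 | 35, p). The expected number of false responders is 35 × 0.93 × a × c.

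| a | c | apparent rate | expected false responders | type I error |
|---|---|---|---|---|
| 0 | – | 0.0700 | 0 | 0.095 |
| 5% | 10% | 0.0747 | 0.16 | 0.117 |
| 5% | 50% | 0.0933 | 0.81 | 0.224 |
| 10% | 10% | 0.0793 | 0.33 | 0.141 |
| 10% | 50% | 0.1165 | 1.63 | 0.387 |

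**One certain false responder.** Four more are then needed among the other 34: P(X ≥ 4 | 34, 0.07) = 0.212. Each such participant adds 1/35 = 2.9 percentage points to the observed rate.

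**Scans after treatment stops.** The Section 10.3.3 window does not close at a new therapy either. However, Section 5.3 bans other anti-cancer therapy on treatment, and the last disease assessment in the Section 9 calendar is the off-treatment visit, 21 ± 7 days after the last dose. This route is therefore limited to that visit or to unscheduled scans.

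**The case against.** The strongest reply is that the path is narrow. Approval is needed. The irradiated lesion must be large enough to bring the whole sum down by 30%, with up to five targets. There must be no new lesion and no non-target progression. The fall must be confirmed. If radiation is needed because the disease has progressed, treatment ends under Section 5.4 and the window closes. A careful assessor could also use the loco-regional wording in Section 10.1.2, or the Unknown category, to set the lesion aside.

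Much of this stands as an argument about frequency, and it is why the size is given as a range. It does not supply a rule. Approval governs whether radiation is given, not how the lesion is scored. Eligibility needs only one measurable lesion (Section 3.1.2), so the irradiated lesion can be the entire sum. The wording that might set the lesion aside is optional, so two sites could score the same case differently.

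Some stronger readings do not hold:
- *A reader might infer that the trial's false-positive rate is 21% or more.* The 0.212 is conditional on one false responder already existing, and the documents give no frequency.
- *A reader might infer that responses under later therapy are a main threat.* The ban on other therapy and the calendar make that route minor.
- *A reader might infer an equal bias in progression-free survival.* New lesions, non-target progression and death still count as events, and that endpoint is secondary with no decision rule.

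**Conclusion.** The gap is real. As written, shrinkage of a target lesion irradiated on study can be counted as a confirmed drug response at any site other than a brain metastasis arising on study, and the effect on the primary response rate is only upward. The size rests on assumed frequencies: a type I error of 0.117 to 0.224 with 5% of participants irradiated on a target lesion and 10% to 50% conversion, and 0.141 to 0.387 with 10% irradiated, against 0.095 for the stated rule. If no target lesion is irradiated, there is no effect. Because the frequency is unknown and several conditions must coincide, this should be fixed, but the documents do not support treating it as a defect that undermines the trial. The point concerns endpoint scoring only, not whether radiation should be given.

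**What to change.** In Section 10.3.3, add a rule for endpoint analysis only:
- For best overall response and its confirmation, only assessments made before the first radiation to a target lesion, or before the start of any other systemic anti-cancer therapy, count toward complete or partial response.
- Radiation confined to non-target lesions does not close the window. Otherwise genuine drug responses in untouched targets would be lost.
- Progression is still recorded after that point.
- The rule governs scoring and does not alter treatment continuation. This is needed because schema note c ties continuation to stable disease or response.

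Add the site and date of any on-study radiation to the Response Assessment Form and to the Appendix H submission list, so that the imaging core can apply the rule.

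The cost is a few sentences and one data item. Sample size and cut-off are unchanged. The downside is that an occasional later response, or one whose confirming scan falls after target-lesion radiation, is not counted, so the reported rate may be slightly lower.
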